1.5 MODIFICATIONS TO THE STATISTICAL SECTION OF THE PROTOCOL

The statistical section of the protocol was never changed in an amendment.

1.6 STATISTICAL MODIFICATIONS MADE IN THE STATISTICAL ANALYSIS PLAN

The endpoint refractory to disease, defined as absence of platelet count doubling after 4 days of standard treatment, and lactate dehydrogenase (LDH) > upper limit of normal (ULN), is not calculated. Patients are missing the necessary timepoints to calculate the endpoint.

2 STATISTICAL AND ANALYTICAL PROCEDURES

2.1 ANALYSIS ENDPOINTS

2.1.1 Demographic and baseline characteristics

For analysis related to the on-study period, the baseline is defined as the screening/baseline visit.

For analysis related to the recurrence period, the baseline value is defined as the recurrence visit of that recurrence episode.

All baseline parameters are presented along with the on-treatment summary statistics in the sections ([Section 2.4.5](#) and [Section 2.4.4](#)).

Demographic characteristics

Demographic variables are:

- Gender at birth: (Male, Female),
- Race: (not allowed to ask / white / black or African American / Asian / American Indian or Alaska native / native Hawaiian or other Pacific islander / other),
- Age in years at inform consent
- Ethnicity (Hispanic, non-Hispanic),

Medical or surgical history

Medical history includes:

- General medical history
- TTP-related medical history: TTP episodes and major thromboembolic events (e.g., myocardial infarction, cerebrovascular accident, pulmonary embolism, deep venous thrombosis, transient ischemic attack, heart failure, unstable angina, coronary revascularization)
- History of hypersensitivity to IMP in study ALX0681-C301

This information will be coded using version 22.0 of Medical Dictionary for Regulatory Activities (MedDRA).

Vital signs

Vital signs at baseline are weight in kilograms, height, blood pressure and pulse (assessed after 5 min in supine position).

Baseline disease characteristics

Baseline disease characteristics are measured at the recurrence visit. It includes:

- ADAMTS13 activity at admission or baseline: <10% / ≥10%
- Baseline organ damage markers: (LDH, TnI and serum creatinine): ≤ULN / >ULN
- Baseline platelet count.
- Baseline RICO activity, vWF:Ag concentration

Any technical details related to computation, dates, and imputation for missing dates are described in [Section 2.5](#).

2.1.2 Prior or concomitant medications

All medications taken from signing of informed consent form until the subject's last visit, immunosuppressive therapies and antithrombotic therapies, are to be reported in the case report form pages.

All medications will be coded using the World Health Organization-Drug Dictionary (WHO-DD) version B3 2019. Based on their start and stop date, prior and concomitant medications will be reported in each analysis period during which they applied (ie, non-treatment emergent (TE) allocation). This implies that each therapy can be reported more than once.

Non-investigational medicinal product

Following medications are the non-investigational medicinal products as the standard of care.

- Plasma exchange (PE)
- Corticosteroid treatment
- Other immunosuppressive treatment

Any technical details related to computation, dates, imputation for missing dates are described in [Section 2.5](#).

2.1.3 Efficacy endpoints

2.1.3.1 TTP recurrence information endpoints

2.1.3.1.1 TTP recurrence presenting symptoms:

TTP recurrence presenting symptoms are assessed at the recurrence visit and collected in the electronic case report form (eCRF). The symptoms categories are fever, fatigue, neurological, gastro-intestinal, bleeding symptoms, cardiac symptoms and others.

2.1.3.1.2 Duration of the TTP recurrence

The duration of TTP recurrence in days (time to platelet count response) is defined as initial platelet count $\geq 150 \times 10^9/L$ with subsequent stop of daily PE within 5 days. The start and end date time of the recurrence, for the calculation of the duration of TTP recurrence, are captured in the eCRF. There will be no imputation of missing data.

2.1.3.1.3 Outcome of the TTP recurrence:

The outcome of the TTP recurrence is assessed at the recurrence follow-up visit and is collected in the eCRF.

2.1.3.2 Treatment outcome endpoints

2.1.3.2.1 Time to platelet count $\geq 150 \times 10^9/L$

Time to platelet count $\geq 150 \times 10^9/L$ is defined as the time from the recurrence visit to the first time the platelet count is $\geq 150 \times 10^9/L$ in the recurrence episode. Patients without an event during the study are censored at the end of the recurrence episode

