[figure not shown]
collected as will safety information (including AEs, safety laboratory parameters, vital signs and physical examination), and determination of PK, ADA, PD parameters (vWF:Ag and RICO), and disease-related markers (ADAMTS13 activity and TnI).

In case of recurrent thrombocytopenia requiring re-initiation of daily PE during an ongoing recurrence period (see [Figure 4](#) and [Table 2](#)), a new visit cycle is to be started, with a recurrence visit on the day of the new recurrence followed by all subsequent visits as indicated in [Table 2](#). All remaining visits of the original schedule are no longer applicable and are not to be performed.

Note: an i.v. loading dose of caplacizumab needs to be administered prior to re-initiation of PE for the recurrence.

Q6M visits that are scheduled within a recurrence period will not be held as assessments at such visits would be confounded by the concurrent recurrence.

Note: Treatment with caplacizumab may not be initiated for subjects who do not fulfil the caplacizumab treatment criteria (see section [3.2.3](#)). Hence, these subjects will be treated with standard of care only. The visit schedule in case of initiation of only standard of care treatment includes a recurrence visit at presentation and a recurrence FU visit at 30 days after end of daily PE (see [Appendix 1](#) for schedule of assessments).

M: month; Y: year

Figure 4: Study flow of Study ALX0681-C302.

Treatment in case of recurrence:

Standard of care treatment (per standard site practice) can include:

- PE with plasma (e.g., fresh frozen plasma, solvent detergent/viral-inactivated plasma, cryosupernatant)
- Corticosteroid treatment
- Use of other immunosuppressive agents (e.g., rituximab)

Initiation of treatment with caplacizumab^{§§}:

Daily PE period

- Loading i.v. dose: subjects will receive a single loading dose of 10 mg study drug by i.v. bolus injection from 6 hours to 15 minutes prior to start of daily PE treatment^{***}.
- Daily s.c. dose: within 2 hours after completing each daily PE, a s.c. injection of 10 mg study drug will be administered daily throughout the full duration of PE treatment.

30-day post-daily PE period

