9. APPENDIX

Appendix 1: Schedule of Assessments in Case of TTP Recurrence (in Case Treatment With Caplacizumab is not Initiated)

Study Period	Recurrence Period (no caplacizumab)	
	Recurrence Visit Recurrence Day 1	Recurrence FU visit 30 days after end of daily PE
TTP recurrence information ^a	X	X
PE information		X
Concomitant medication		→
Adverse events		→
Supine heart rate & blood pressure ^b	X	X
Physical examination	X	X
SF-36		X
Clinical laboratory analyses + urinalysis ^c	X	X
Organ damage markers: TnI ^d	X	X
ADAMTS13 activity ^d	X	X
Immunogenicity (ADA panel) ^d	X	
PD parameter : vWF:Ag ^d	X	X

^a TTP recurrence information includes presenting symptoms (assessed at recurrence visit), duration and outcome (assessed at the recurrence FU visit).

^b Heart rate and blood pressure to be assessed after 5 min in supine position.

[figure not shown]
^c Clinical laboratory analyses include hematology (Hb, Hct, RBC, WBC, platelets); chemistry (AST, ALT, LDH, creatinine, protein, cholesterol and CRP). Urinalysis includes assessment of albumin. The results of assessment of platelet count and LDH levels performed as per standard of care (by a local laboratory) at any time during the recurrence period will be collected in the eCRF, if available.

^d Samples need to be collected prior to start of the first PE treatment.

Signature Page

This is a representation of an electronic record that was signed electronically in Livelink.
This page is the manifestation of the electronic signature(s) used in compliance with the organizations
electronic signature policies and procedures.

Date: [Redacted]

Meaning: Approved

=====

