The visit schedule upon initiation of treatment consists of a recurrence visit at presentation, a visit on Day 3 of treatment with caplacizumab, weekly visits during treatment with caplacizumab (starting 1 day after the last daily PE), and a recurrence FU visit 1 week after the end of treatment with caplacizumab. At these visits, information with regard to the TTP recurrence (presenting symptoms, duration, and outcome) and treatment choice will be collected as will safety information (including AEs, safety laboratory parameters, vital signs and physical examination), and determination of pharmacokinetic [PK], ADA, pharmacodynamic [PD] parameters (vWF:Ag and Ristocetin cofactor activity [RICO]), and disease-related markers (ADAMTS13 activity and Tnl).

In case of recurrent thrombocytopenia requiring re-initiation of daily PE during an ongoing recurrence period (see [Figure 1](#)), a new visit cycle is to be started, with a recurrence visit on the day of the new recurrence followed by all subsequent visits as indicated in [Table 5](#). An i.v. loading dose of caplacizumab needs to be administered prior to re-initiation of PE for the recurrence. All remaining visits of the original schedule are no longer applicable and are not to be performed.

Q6M visits that are scheduled within a recurrence period will not be held as assessments at such visits would be confounded by the concurrent recurrence. Treatment with caplacizumab may not be initiated for subjects who do not fulfil the caplacizumab treatment criteria. Hence, these subjects will be treated with standard of care only. The visit schedule in case of initiation of only standard of care treatment includes a recurrence visit at presentation and a recurrence FU visit at 30 days after end of daily PE (see [Table 6](#) for schedule of assessments).

Figure 1 - Study flow of study ALX0681-C302

M: month; Y : year

Treatment in case of recurrence:

Initiation of treatment with caplacizumab is for subjects with a clinical diagnosis of an episode of recurrent acquired TTP requiring initiation of daily PE treatment and who had a baseline visit.

Treatment with caplacizumab is not permitted for subjects who:

- Are pregnant or intend to get pregnant in the near future
- Have a history of a severe and/or serious hypersensitivity reaction to investigational medicinal product (IMP) in Study ALX0681-C301 or Study ALX0681-C302.

Standard of care treatment (per standard site practice) can include:

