2.4.4 Analyses of efficacy endpoints

All efficacy endpoints related to assessments on the Q6M FU visits will be analyzed using the ITO population. Summarization will be conducted on the total study population and by analysis group. For the group-wise analysis, the following groups will be considered:

- caplacizumab-treated: defined as subjects in the ITO population who have been randomized to caplacizumab in study ALX0681-C301, evaluated up to their first recurrence in the ALX0681-C302 trial;
- standard of care-treated, defined as subjects in the ITO population who have been randomized to placebo in study ALX0681-C301, evaluated up to their first recurrence in the ALX0681-C302 trial.

Subjects who had a recurrence during study ALX0681-C301 or between the Final (28 day) FU visit in study ALX0681-C301 and Screening/Baseline in study ALX0681-C302, will not be considered for the group-wise analyses.

All efficacy endpoints related to assessments during the recurrence period will be analyzed using the recurrence population. The effect of retreatment of caplacizumab on these endpoints will be evaluated. For the group-wise analysis the following groups are considered, unless otherwise specified:

- Treated with IMP: defined as subjects in the recurrence population who received caplacizumab in the ALX0681-C302 during a recurrence episode
- Not treated with IMP: defined as subjects in the recurrence population who did not receive caplacizumab in the ALX0681-C302 during a recurrence episode.

Of note, depending on the recurrence episode, the same subject can appear in both analysis groups.

Select sensitivity analyses may be planned to assess the effect of heterogeneity in the timings of the baseline visit between subjects. Unless specified otherwise, no missing data imputation will be applied, and all efficacy endpoints will be analyzed as observed.

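### Time to platelet count ≥150 by caplacizumab use can be dated late in untreated episodes, because between presentation and 30 days after plasma exchange they have no protocol count

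*SAP*

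**What the plan says.** The endpoint (SAP 2.1.3.2.1) "is defined as the time from the recurrence visit to the first time the platelet count is" 150 × 10⁹/L or more. For episodes without an event: "Patients without an event during the study are censored at the end of the recurrence episode". SAP 2.4.4.5.1 reports Kaplan-Meier quartiles with 95% CIs and a plot.

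SAP 2.4.4 intends to evaluate the effect of retreatment on recurrence-period endpoints. It sets two default groups at episode level, and the second is "Not treated with IMP: defined as subjects in the recurrence population who did not receive caplacizumab in the ALX0681-C302 during a recurrence episode". Section 2.4.4.5.1 names no other grouping. Endpoints are analysed as observed, without imputation.

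The visit schedules differ by group:

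- Treated episodes: besides presentation and follow-up, SAP 1.4 lists "a visit on Day 3 of treatment with caplacizumab, weekly visits during treatment with caplacizumab (starting 1 day after the last daily PE"). Protocol Table 2 and SAP Table 5 place a laboratory draw at each of these visits.
- Untreated episodes: the schedule "includes a recurrence visit at presentation and a recurrence FU visit at 30 days after end of daily PE" (SAP 1.4; likewise Protocol 3.1.1, Protocol Appendix 1 and SAP Table 6).

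For both groups, local standard-of-care platelet and LDH results obtained "at any time during the recurrence period will be collected in the eCRF, if available" (Protocol Appendix 1 footnote c; the same rule is in Table 2 footnote e). SAP 2.5.5 lets unscheduled measurements feed time-to-event endpoints. SAP 1.6 drops the refractory-disease endpoint, giving as reason: "Patients are missing the necessary timepoints to calculate the endpoint".

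**The concern.** The event date is the date of the first recorded count at or above the threshold, so it depends on when counts are recorded as well as on when the platelets recover. In a treated episode, protocol draws cap the delay even if no local count is entered. In an untreated episode nothing in the protocol caps it until 30 days after daily PE. Two episodes with the same recovery can therefore have very different event dates, and the difference runs in favour of caplacizumab if local counts are equally complete in both groups.

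The SAP has no safeguard. It sets no minimum count frequency, plans no report of count completeness or source, and does not use the last count below the threshold to bound the response time. At stake is how the by-group medians and curves are read as evidence on repeated use, which is one of the study objectives.

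**Working it through.** The plan gives no sample size, expected median or event count for this endpoint, so there is no figure to reproduce. The check asks how far the schedule alone can separate two groups with identical recovery.

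**Single-episode arithmetic, protocol counts only.** Let E be the day of the last daily PE, with presentation and first dose on Day 1. If the count crosses 150 after the Day 3 visit:

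- treated event day = E + 1
- untreated event day = E + 30
- artefact = (E + 30) − (E + 1) = 29 days, whatever E is

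Example: true response on Day 5, with E = 7 (two days later, in line with the background text in Protocol 1.1.1). The recorded days are 8 and 37. What the data actually support is an interval: Day 3 to Day 8 in the treated episode (8 − 3 = 5 days wide) and Day 1 to Day 37 in the untreated one (37 − 1 = 36 days wide). Both contain Day 5. The Kaplan-Meier analysis uses only the right-hand ends.

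**Effect of partial local counts.** Simulation of 200,000 episodes per group with the same true response distribution in both.

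- From the protocol: median true response of 2.97 or 4.79 days (the two phase II medians in Protocol 1.2.4, used only for scale), and a 2-day gap from response to the end of PE (Protocol 1.1.1).
- Assumed: Weibull shape 1.5; gaps of 3 and 5 days as alternatives; and a share f of episodes with daily local counts in the eCRF, equal in both groups, the remaining episodes having none.

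Ranges are over the six combinations of median and gap:

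| f | Treated median (days) | Untreated median (days) | Difference in means (days) |
|---|---|---|---|
| 0 | 6–11 | 35–40 | 29.4–30.8 |
| 0.25 | 6–10 | 35–39 | 22.1–23.1 |
| 0.5 | 5–9 | 15–36 | 14.7–15.4 |
| 0.6 | 4–8 | 6–10 | 11.8–12.4 |
| 0.75 | 4–6 | 5–7 | 7.4–7.7 |
| 0.9 | 4–6 | 4–6 | 2.9–3.1 |
| 1 | 3–5 | 3–5 | 0 |

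Within each combination the gap in medians is 29 days at f = 0, 2 to 3 days at f = 0.6, 1 day at f = 0.75, and nil at f = 0.9 and above. For scale, the phase II contrast was 4.79 − 2.97 = 1.82 days, for confirmed normalization, which is a different endpoint.

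**Unequal availability.** The direction depends on f being similar in the two groups. With complete local counts in untreated episodes and none in treated ones, the same table gives 3–5 days untreated (f = 1) against 6–11 treated (f = 0), which is the reverse order.

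**The case against.** The strongest reply is that the plan already collects what is needed. The definition is not limited to scheduled or central-laboratory counts. Both schedules carry the same instruction to enter local counts, and SAP 2.5.5 uses them. Such counts very likely exist: Protocol 1.1.1 ties the end of daily PE to platelet normalization, and Protocol 3.3.6, written for caplacizumab episodes, expects hospitalization during daily PE. This stands. The 29 days is a worst case, and with largely complete local counts the medians barely differ.

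Three stronger readings are tempting, and the documents do not support them:

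- *Untreated response is certain to be dated late.* This depends on how complete the local counts are, which neither document states.
- *SAP 1.6 proves that the early platelet counts are missing.* The dropped endpoint needed platelet doubling at a fixed time, after 4 days, plus LDH. Neither schedule fixes a visit at that time, and SAP 1.6 does not say which test was missing or in which group. It warns of gaps but does not show that they differ between groups.
- *This is a main efficacy measure.* Platelet response is not among the Main Endpoints in the protocol synopsis. It is a treatment-outcome item, and SAP 2.4.4.8 rules out formal testing.

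SAP 2.1.3.1.2 also defines duration of recurrence from start and end date-times captured in the eCRF. That is a partial cross-check, but it does not correct the curve for this endpoint.

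What the reply leaves open is that the rule permits the use of local counts without ensuring that they are entered, and any gap costs more in untreated episodes. A descriptive median is still misread if the visit schedule has moved it.

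**Conclusion.** The concern holds in conditional form. The difference in protocol counts is plain in both documents, and so is the default by-group Kaplan-Meier summary. Where local counts are incomplete, response in untreated episodes can be dated late and the descriptive curves can favour caplacizumab.

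If local-count availability is the same in both groups, the artefact in the median lies between zero (complete daily local counts) and about 29 days (none). It is 2 to 3 days or less once about 60% of episodes have daily counts. These intermediate figures rest on the assumed Weibull shape, PE gap and all-or-none pattern of local counts. The 29 days rests only on the schedules and a response after the Day 3 visit. Where in the range this study falls cannot be settled from the documents. The matter deserves a change to the SAP because the safeguard is cheap, but it does not touch a main endpoint.

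**What to change.** In SAP 2.4.4.5.1:

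- (a) Analyse the by-group endpoint as interval-censored between the last count below 150 and the first count at or above 150, at least as a sensitivity analysis beside the Kaplan-Meier curve.
- (b) Tabulate by group the number and source (local or central) of platelet counts per episode, and the width of the interval containing the response.
- (c) Before database lock (planned for December 2020, SAP section 4), query sites for existing local platelet counts from presentation to the end of daily PE.

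No new visits or blood draws are needed. The cost is some retrieval work at sites and wider intervals where records are thin. The untreated group is likely to be small. It is not randomized and is selected by the treatment criteria in Protocol 3.2.3 (pregnancy or intended pregnancy, earlier severe or serious hypersensitivity, no baseline visit). The change removes an artefact of dating but does not make the two groups comparable, and the report should say so beside the curves.

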2.1.3.2.2 Duration of daily PE

Duration of daily PE in a recurrence episode is calculated as end date of daily PE – start date of daily PE + 1 day.

2.1.3.2.3 Number of days in hospital:

The number of days in hospital is calculated as hospitalization discharge date – hospitalization admission date + 1 day.

2.1.3.2.4 Number of days in intensive care unit:

The number of days in intensive care unit (ICU) is calculated as ICU discharge date – ICU admission date + 1 day.

2.1.3.3 Cognitive assessment

2.1.3.3.1 Repeatable Battery for the assessment of Neurological Status (RBANS)

The RBANS is a 30-min comprehensive screening test with five individual domains (immediate memory, delayed memory, attention, language, and visuospatial ability) to examine the cognitive mental status of a subject. The results of the RBANS are reported as a total scale (overall score) and scores for each individual domain, based on the normal population values adjusted for age, provided by the RBANS manual. The overall score is a summary of performance across all five

individual domain scores. Scores are standardized to a mean score of 100 with a standard deviation of 15.

2.1.3.4 Quality of life

2.1.3.4.1 Headache impact test-6 (HIT-6)

The HIT-6 questionnaire is an easy to administer assessment that can be used as a clinical evaluation of the impact of headache on a patient's quality of life in both clinical practice and clinical research.

The questionnaire includes 6 questions covering the 6 areas of functioning most impacted in headache sufferers including pain, role functioning (the ability to carry out usual activities), social functioning, vitality (energy/ fatigue), cognitive functioning, and psychological/emotional distress. Scores range from 36 to 78, with higher scores reflecting worse condition.

2.1.3.4.2 Short Form Health Survey (SF-36)

The Short Form-36 (SF-36) version 2.0 is a 36 items questionnaire that measures Quality of Life (QoL). It has eight multi-item scales:

- Physical Functioning (10 items)
- Social Functioning (2 items)
- Role Functioning/Physical (4 items)
- Role Functioning/Emotional (3 items)
- Emotional Well-Being (5 items)
- Energy/Fatigue (4 items)
- Pain (2 items)
- General Health (5 items).

There is an additional single item covering change in health status over the last year.

Scales are set up so that a higher score indicates better health. Eleven items are reverse scored so that a higher precoded item value indicates a poorer health state. Those items are recoded before being added to other items on the same scale. Therefore, for each dimension, item scores are coded, summed, and transformed on to a scale from 0 (worst possible health state measured by the questionnaire) to 100 (best possible health state).

